7.5.1 Neurapheresis Therapy Rates

Neurapheresis therapy will commence slowly at a nominal flow rate of 0.5mL/min. to accommodate the volume of hemorrhagic CSF pooled in the lumbar cistern. An increase of flow shall not occur until 1 hour of aggregate pump time has elapsed to optimize the system operation during the initial access of the pooled hemorrhage. At this time, a baseline CSF sample will be taken, see Section 7.5.7.

After the CSF sample has been taken, the MNeuro CFS will transition the system to auto mode. In this mode, an automated algorithm will adjust the flow rates to continuously optimize the Neurapheresis therapy based on system pressures. The MNeuro CFS will be present while the system is in auto mode for system oversight. During study therapy, the waste rate will be generally maintained within a range of 12-15 mL/hr as determined by the Investigator. However, at any time the Investigator may choose to manually adjust the system waste rate based on subject status.

7.5.2 Neurapheresis Termination Criteria

Investigators should engage in an ongoing dialogue with the MNeuro CFS to address starting and stopping the pump for CSF sampling, change in clinical status, emergent situations and SOC concerns e.g., transport, extubation, physical therapy, study-required neuro checks or other. If a subject meets any of the criteria below, Neurapheresis should be stopped immediately (if not previously stopped) and the subject should be scheduled for catheter removal.

Change(s) in Subject conditions that require Neurapheresis termination are:

- Brainstem herniation
- Lower extremity paralysis
- Subdural spinal hematoma

- Subdural hematoma or hygroma
- Abnormal gram stain
- Re-bleeding event requiring intervention e.g., re-coiling, re-clip
- Subject previously non-intubated/extubated requires new or re-intubation
- ICP is greater than Lumbar pressure at five consecutive study-required neuro checks
- Subject requires inversion (such as Trendelenburg position)

As the MNeuro CFS will be on site during Neurapheresis therapy, the sponsor will be notified immediately if any subject has the Neurapheresis procedure terminated due to reasons above. Source documents may be requested for the Sponsor to adequately review the termination.

The Investigator may pause the system or terminate the procedure at any time. The Subject also has the right to terminate the procedure at any time. If study therapy must be terminated early, a head CT within (\pm 4hr) of catheter removal must be obtained to document the final amount and location of blood within the basal cisterns to allow for comparison to baseline.

7.5.3 Role of the MNeuro Clinical Field Specialist (CFS)

MNeuro clinical field specialists or their trained representatives are responsible for training and directing the applicable site staff in the placement, assembly, priming, replacement and removal of all components of the Neurapheresis System. The MNeuro CFS is also responsible for the general operation and trouble-shooting of the investigational system under guidance from Investigators and site staff to confirm the system does not present any care concerns and is functioning properly. The attending MNeuro CFS or representative will not practice medicine, alter data or make any clinical suggestions based on collected data or observed data trends.

During the Neurapheresis procedure, the MNeuro CFS is also responsible for addressing any system alert states. System data includes but is not limited to, inlet and return pressure(s), flow and waste rates, processed volume etc. System data collected during a Neurapheresis procedure will be recorded on the LabView Software and is saved to the PC hard drive and retrieved to USB pen drives. The MNeuro CFS will also help the site staff document the lumbar pressure from the system during the study-required neuro checks.

If the system experiences an issue e.g., pump failure, filter clot, catheter kink or obstruction, breach of sterility etc., MNeuro CFS or representative will facilitate replacement or removal of the affected component after discussing “next steps” with the Investigator.

7.5.4 CSF Pressure Guidance During Neurapheresis

Subjects must have an EVD as part of the SOC for post SAH intracranial pressure management. Study Investigators should consult with the MNeuro CFS to coordinate the EVD maintenance with the Neurapheresis System waste control rate. Investigators are asked to clamp the EVD and open if ICP goes to ≥ 20 mmHg while the Neurapheresis system is operating. The Investigator has the medical discretion to open the EVD at a lower pressure limit as clinical status for a specific subject may require. Alternatively, the Investigator may increase the therapy waste rate to manage an increasing trend in ICP with the Neurapheresis system rather than open the EVD. If the EVD is opened, it should be set to a pressure of 20 mmHg. Also, the Investigator may reduce the system waste rate or pause the system if unusually low ICP or clinical symptoms indicate continued drainage at the current rate may be unsafe.

Brain herniation is a known risk for intracranial hemorrhage patients, including aneurysmal subarachnoid hemorrhage, as the blood can create excess pressure in the brain. Likewise, herniation is a known risk of lumbar drainage as it may lead to cranial pressure changes.

SAH patients with increased risk for herniation may include those with:

- CNS infection or abscess;
- Excessive cranial edema/swelling that increases mass effect;
- Hydrocephalus or other complication that could compromise CSF communication;
- Other mass effect (tumor, hematoma, etc.) that may lead to high intracranial pressure (ICP);
- A sustained negative pressure change between intracranial and lumbar pressure due to high ICP or low lumbar pressure.

During Neurapheresis therapy, the protocol requires measurement of both lumbar pressure and ICP for assessment of subject status administered hourly (± 1 hr). This should be performed at the same time as the study required neurological assessments. Centers will not be deviated for obtaining ICP measurements at a greater frequency if that is the center SOC. ICP is to be captured on the applicable CRF. It is acceptable to have the attending critical nursing staff obtain the measurements if that is the SOC of the center's critical care unit.

To ensure accurate pressure measurements, the system will be paused, and the inlet pressure sensor will be leveled to the lumbar region of the subject. The lumbar pressure will then be recorded. The site staff will use their normal process for leveling and recording the ICP measurement. The system will remain paused if the lumbar pressure falls below 4.4 mmHg (6.0 cmH₂O), and the Investigator will be notified to review clinical symptoms and system data prior to restarting. Alternatively, if the Investigator has pre-defined and documented a treatment plan, the system may be re-started according to the plan and on-going communication with the Investigator maintained to ensure adequate oversight of subject safety.

If during any pressure check the ICP recorded is higher than the lumbar pressure taken at the same neuro check, the system will remain paused until the ICP is equal to or lower than the lumbar CSF pressure for at least two consecutive neuro checks AND the Investigator has approved restarting the system. If the ICP remains higher than the lumbar pressure for five consecutive study-required neuro checks, then therapy will be terminated, and the site should prepare to gather the end of treatment data.

In cases where the Neurapheresis procedure is terminated early, the protocol required *ICP measurements are to be continued* until the catheter has been removed.

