
Neurapheresis Surveillance
	
Following aneurysm securement and prior to initiating study therapy, a head CT is required to establish safety for beginning study therapy as well as provide a baseline to which the follow-up CTs may be compared. This may be done following catheter placement but needs to be done in a department scanner.
 
Subjects will be monitored regularly during study therapy according to institutional SOC for Neuro ICU monitoring with additional protocol requirements as defined below. Protocol required neuro monitoring should begin following catheter securement. The catheter can remain in-dwelling for up to 72 hours ($\pm 4\text{hr}$) in Treated Subjects during which study therapy can be performed.
 
 • Intracranial pressure (ICP), Glasgow coma score (GCS), Lumbar pressure and Peripheral checks performed hourly ($\pm 1\text{hr}$) while the catheter is in-dwelling • CSF Sampling every 8 hours while the catheter is in-dwelling • Venous blood sample will be taken at 36 hours and 72 hours or end of catheter in-dwelling ($\pm 4\text{hr}$) 
To ensure the pressures are accurately obtained, the system will be paused temporarily for completion of each study-required neuro check. If the lumbar pressure reads below 4.4 mmHg (6.0 cmH₂O), the Investigator will be notified for review of clinical symptoms and system data prior to re-starting therapy unless a pre-defined treatment plan has already been directed by the Investigator.
 
If the ICP recorded at a study-required neuro check is higher than the lumbar pressure at the same neuro check. The system should remain paused until the ICP is equal to or lower than lumbar pressure for at least two consecutive neuro checks and the Investigator has approved restarting the system.
 
Additionally, at 36 hours and 72 hours or end of catheter in-dwelling ($\pm 4\text{hr}$), a head CT will be required. The CTs must be taken using a department scanner and will be used to compare to the baseline CT and document the amount of blood removal from the basal cisterns for the primary endpoint.
 
Additional data related to the clinical status of the subjects will be collected throughout study therapy such as the development of complications or study adverse events.

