7.5.9 Patient Transport during Neurapheresis

If it is necessary to transport the study subject during the Neurapheresis procedure, ensure that the Sponsor's representative is present and the system is stopped for transport. Care should be taken to protect the integrity of tubing connections during transport. If possible, transport the system connected to the Subject, keeping the fluid loop intact or, remove the tubing and filters from the mounting bracket and place the components on the bed. If a system disconnect is required, connect the two catheter ends to one another (male→female) keeping the catheter sterile, see Figure 7. If sterility is compromised when connecting, the ends of catheter should be cleansed with Betadine for three minutes per AANA guidelines or SOC at center for sterile line technique when reconnecting to the Neurapheresis System.

The patient may sit up, stand, or move from their hospital bed as permitted or recommended by SOC. Center personnel should work with the MNeuro CFS to position the system cart in such a way to minimize strain on the catheter and tubing and allow proper movement of the patient. The system should remain connected to the patient, and depending on the type of movement, the system may continue running.

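### Section 7.5.4 compares lumbar pressure and ICP as raw readings taken at different reference levels with no stated body position, so a raised head can hide the gradient the pause, restart and termination rule is meant to detect.

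*Combined protocol and SAP*

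**What the plan says.** Section 7.5.4 pauses the system at each hourly check so that pressures are measured accurately. The two readings have different references. For the lumbar reading, "the inlet pressure sensor will be leveled to the lumbar region of the subject". For ICP, "The site staff will use their normal process for leveling and recording the ICP measurement".

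The recorded values are then compared directly:

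- **Pause and restart.** If ICP is above lumbar pressure at a check, the system stays paused until "ICP is equal to or lower than the lumbar CSF pressure for at least two consecutive neuro checks" and the Investigator approves.
- **Termination.** Section 7.5.2 ends therapy when "ICP is greater than Lumbar pressure at five consecutive study-required neuro checks".

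The Synopsis repeats both rules. Neither it, 7.5.2, 7.5.4 nor the footnotes to Table 4 gives a body position, a common zero level or a height correction. Inversion such as Trendelenburg ends therapy under 7.5.2, but head-up positions are not restricted. Section 7.5.9 says "The patient may sit up, stand, or move from their hospital bed as permitted or recommended by SOC" and adds that "depending on the type of movement, the system may continue running".

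Section 7.4 refers system set-up to the IFU. Section 7.5.3 has the field specialist "help the site staff document the lumbar pressure from the system during the study-required neuro checks". Section 7.5.4 cites no IFU step for levelling or position.

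**The concern.** Two pressures in one fluid column can be compared only if they are read at the same height or corrected for the difference. Pausing the pump removes the pump's effect on the readings but not the height difference. If ICP is zeroed at the head and the head is raised, the lumbar reading carries the weight of the fluid column between the two points. It then exceeds ICP even when there is no gradient.

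The error is in the unsafe direction. It makes ICP above lumbar harder to record and makes ICP at or below lumbar easier to record, which is the condition for restart.

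The rule addresses a hazard already seen. Section 7.5.4 lists a sustained negative intracranial-to-lumbar pressure change among the herniation risks. Section 2.2 reports one herniation in 16 treated subjects and attributes it to evolving mass effect combined with a device-created gradient of this kind. Subject safety is at stake here; no efficacy analysis is affected.

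**Working it through.** **Inputs from the protocol.** Lumbar reference: the lumbar region. ICP reference: each site's own. Margin: zero (any excess of ICP over lumbar trips). Restart: two clear checks plus Investigator approval. Termination: five consecutive trips.

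**Assumptions, not in the documents.** ICP is zeroed at the head. The fluid column is static and communicating. CSF density is 1.00 to 1.01 times water. Let h be the height in cm from the lumbar sensor up to the ICP zero point.

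**The plan's own conversion.** 1 cmH2O = 98.0665/133.322 = 0.7356 mmHg, so 6.0 cmH2O = 4.41 mmHg. Section 7.5.4 states 4.4, which agrees.

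**Offset.** With no gradient, lumbar = ICP + 0.7356 × h. The true ICP excess is therefore G = ICP + 0.7356 × h − lumbar, while the rule uses ICP − lumbar = G − 0.7356 × h.

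| h (cm) | Offset (mmHg), density 1.00 to 1.01 |
|---|---|
| 0 | 0 |
| 10 | 7.36 to 7.43 |
| 20 | 14.71 to 14.86 |

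**Height that hides a given excess** (G/0.7356, density 1.00): 3 mmHg at 4.1 cm, 5 mmHg at 6.8 cm, 10 mmHg at 13.6 cm.

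**Effect on the rule for G = 4 mmHg:**

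- h = 0: 4 − 0 = +4.0, pause.
- h = 5 cm: 4 − 3.68 = +0.3, pause.
- h = 10 cm: 4 − 7.36 = −3.4, no trip, and the check counts toward restart.

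The same true gradient thus gives opposite decisions according to posture. Raising the head between checks could supply the two clear checks, or interrupt a run of five.

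**Illustration with assumed readings.** ICP 12 mmHg, lumbar 15.4 mmHg, h = 10 cm. The true excess is 12 + 7.4 − 15.4 = 4.0 mmHg. The gradient rule does not trip (12 is below 15.4), the EVD threshold of 20 mmHg is not reached, and the lumbar floor of 4.4 mmHg is not crossed.

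**Checking the obvious remedy.** Suppose the corrected difference ICP + 0.74 × h − lumbar were used with the present zero margin. A 2 cm error in h moves it by 2 × 0.7356 = 1.5 mmHg. In a subject with no gradient it is centred on zero, so with symmetric error about half of checks trip. If errors are independent between checks (an illustrative assumption), the probability q(n) of no run of five trips in n checks satisfies q(n) = q(n−1)/2 + q(n−2)/4 + q(n−3)/8 + q(n−4)/16 + q(n−5)/32, with q(0) to q(4) equal to 1. The chance of at least one terminating run, 1 − q(n), is 30% over 24 checks, 43% over 36 and 69% over 72. The corrected difference therefore needs a tolerance. Flat readings are centred on zero in the same way.

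**The case against.** The strongest reply is that the harm depends on facts the documents do not give: ICP zeroed at the head, the head above the lumbar sensor at the moment of reading, and no instruction elsewhere. Section 7.4 places set-up in the IFU, 7.5 requires training, and 7.5.3 puts a field specialist at the bedside. A levelling or position step could well be in that material. This stands and limits the confidence. It does not remove the point, because 7.5.4 does state how each pressure is referenced, and what it states does not give a common level.

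A reader might infer from 7.5.9 that checks are taken with the subject sitting or standing. The section does not say so. It concerns transport and mobilisation, and shows only that head-up posture is not generally restricted. A reader might also infer that mismatched levelling contributed to the herniation in Section 2.2. The documents do not say how pressures were levelled in that subject, and they name mass effect as a joint cause.

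Other safeguards exist: EVD opening at ICP of 20 mmHg or more, the 4.4 mmHg lumbar floor, hourly GCS and peripheral checks, the motor-GCS pause in intubated subjects (7.5.6), the baseline and 36-hour CTs, and Investigator approval to restart. They reduce the risk, but none compares the two pressures on a common reference. Investigator approval is required only once the rule has tripped.

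The objection that a zero-margin height correction would cause many false trips is right, and the fix below takes account of it.

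**Conclusion.** The point holds conditionally and should be fixed, with medium confidence. As written, 7.5.4 compares two pressures that need not share a reference level. If ICP is zeroed at the head and the head is raised, the rule misses any true ICP excess smaller than about 0.74 mmHg per cm of height. The offset is zero when the subject is flat or both pressures are read at one level. A site with another ICP zero point would have a different offset, so the rule may also act differently across the up to 8 centers.

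The documents contain no ICP zero points, heights, bed angles or paired readings. They do not support a claim that gradients have been missed, or any estimate of how often that would happen.

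**What to change.** In 7.5.4, and wherever the rule is repeated:

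1. Require both readings at every neuro check to be taken in one stated position, flat where tolerated, and record the position on the CRF.
2. Where the subject cannot lie flat, record h and use the difference ICP + 0.74 × h − lumbar. The sponsor and DSMB should set a tolerance for measurement error before this difference drives a pause or termination. They should also reconfirm the zero margin for flat readings.
3. Keep each site's usual ICP reference for the 20 mmHg EVD rule.
4. If the IFU already fixes position and level, cite it in 7.5.4; that may be all that is needed.

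The cost is protocol wording, site training, one or two CRF fields and a short repositioning or measurement at each hourly check. More pauses are possible because gradients now hidden would trip the rule. With 16 of 30 subjects already treated under a previous version, the change could apply to at most 30 − 16 = 14 more.

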7.5.5 Neurologic Assessments During Neurapheresis

During Neurapheresis therapy, the protocol requires neurological assessments including GCS and Peripheral neurological checks for assessment of subject status to be administered hourly (± 1 hr). Peripheral neurological checks will include assessment of leg strength and sensory changes to identify potential adverse events such as subdural spinal hematoma. Centers will not be deviated for performing assessments at a greater frequency if that is the center SOC or if additional assessments are administered. Assessments are to be captured on the applicable CRF. It is

acceptable to have the attending critical nursing staff conduct the assessments if that is the SOC of the center's critical care unit. The Investigator may reduce the system waste rate or pause the system if clinical symptoms indicate continued drainage at the current rate may be unsafe.

In cases where the Neurapheresis procedure is terminated early, the protocol required neurological assessments are to be continued until the catheter has been removed.

Neurological monitoring is required hourly during study therapy and similar to standard practice, this monitoring is intended to identify changes to neurological status that may be suggestive of neurological decline. Note that the protocol requires that study therapy be stopped if herniation is identified, regardless of whether the Investigator believes the herniation to be related to study therapy.

7.5.6 Neurologic Assessments for Intubated Subjects

To ensure the identification of deterioration in intubated subjects, the following data collection and criteria related to the GCS are established to pause the Neurapheresis procedure and allow for adequate assessment of the subject's status. Specifically, GCS will be captured each hour while the subject is intubated.

GCS should be captured noting that the subject is intubated (t) and it would be expected that the highest score for an intubated subject will be 10(t) due to inability to provide a verbal response. Further, Neurapheresis is required to be paused in an intubated subject if the motor component of the GCS drops below 6. Neurapheresis can begin upon improvement in the motor component score back to 6 or at a motor component of 5 that is stable for at least 4 consecutive hours during which a cause for the deficiency is identified such that the investigator concludes is not related to Neurapheresis. If the motor component or total GCS score continues to decline Neurapheresis should be terminated and the subject scheduled for catheter removal.

Finally, if a subject who was previously extubated/non-intubated requires new or re-intubation, Neurapheresis is to be terminated.

7.5.7 CSF Sampling During Neurapheresis

During catheter in-dwelling and Neurapheresis therapy, CSF samples will be obtained at regular intervals until the catheter is removed. A maximum of 11 CSF samples total per subject will be taken. Ten of those during catheter indwelling, though fewer may be taken if the catheter must be removed early.

Samples will be taken according to the schedule in Table 10 below. The initial CSF sample will be taken during catheter placement however, the first sample taken during catheter in-dwelling will be considered the Baseline CSF sample (pre-Neurapheresis sample) to which the later samples will be compared. The last CSF sample taken will be considered the Final sample or (post-Neurapheresis sample) which will be compared to the Baseline sample for applicable endpoint analyses. To account for different assay requirements, CSF sample volumes are different for the initial and seventh (40 hr) sample than those in between.

It is allowable to collect less CSF sample volume for completion of the Cell counts with Differentials based on site specific laboratory requirements. Current laboratory certificates are

required by the sponsor with laboratory processes to be made available upon request. Care should be taken to ensure laboratory samples are handled and processed consistently for accurate data reporting.

During catheter in-dwelling, the first sample (#2 on Table 10 below) should be taken after 1 hour ($\pm 30\text{min}$) of Neurapheresis therapy. The MNeuro CFS will assist in monitoring the therapy time in order to prepare for the sample. The next CSF sample should be taken at 8 hours ($\pm 2\text{hr}$) from catheter securement (8 hours of catheter in-dwelling) then each subsequent sample taken every 8 hours ($\pm 1\text{hr}$) from the previous scheduled sample (i.e. every 8 hours during catheter in-dwelling).

Table 3: Required CSF Samples

Sample #	Sample Metric	Required Assay	CSF Sample Volume
1	During Catheter Placement (needle stick)	Cell counts with Differential: RBC, WBC, neutrophils, lymphocytes, etc. Chemistries: Total protein, Glucose, Culture	3ml
		CSF Biomarkers (requires -80° storage until shipped) ^β	2ml ^β
2	1hr ($\pm 30\text{min}$) of Neurapheresis	Cell counts with Differential and Chemistries	3ml
3	8hr ($\pm 2\text{hr}$)*	Cell counts with Differential and Chemistries	3ml
4	16hr ($\pm 2\text{hr}$)*	Cell counts with Differential and Chemistries	3ml
5	24hr ($\pm 2\text{hr}$)*	Cell counts with Differential and Chemistries	3ml
6	32hr ($\pm 2\text{hr}$)*	Cell counts with Differential and Chemistries	3ml
7	40hr ($\pm 2\text{hr}$)*	Cell counts with Differential and Chemistries	3ml
		CSF Biomarkers (requires -80° storage until shipped)	2ml
8	48hr ($\pm 2\text{hr}$)*	Cell counts with Differential and Chemistries	3ml
9	56hr ($\pm 2\text{hr}$)*	Cell counts with Differential and Chemistries	3ml
10	64hr ($\pm 2\text{hr}$)*	Cell counts with Differential and Chemistries	3ml
11	72hr ($\pm 2\text{hr}$)* ^γ	Cell counts with Differential and Chemistries	3ml

*time measured from catheter securement (beginning of indwelling time)

^βif a CSF sample for biomarkers was not obtained during catheter placement (sample #1), it can be done with sample #2

^γif the catheter is removed prior to reaching the 72hr indwelling limit, a final CSF sample should be taken just prior to catheter removal

Center personnel shall work with the MNeuro CFS to time the CSF sampling as to not interfere with SOC patient care. To ensure sample consistency and minimize subject impact, samples are to be taken using the automated sampling process within the system. The system is switched to “sample mode” then using sterile technique, a syringe is inserted into the three-way sample stopcock. Sample mode should be set at the nominal flow rate of 0.5ml/minute. The system will automatically fill the syringe. Once the appropriate amount of CSF has been retrieved, sample

mode can be stopped and the syringe removed. The MNeuro CFS will pause the system prior to the sample acquisition, and will leave the system paused for a short period post sampling e.g., approx. 15 min, to allow for the CSF fluid balance to recover.

Also reference the IFU for additional details in regard to CSF sampling. A de-identified laboratory print-out of the required CSF assay analyses must be provided to the Sponsor. The original laboratory results must be available for monitoring.

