7.4.1 Catheter Insertion Highlights

- Soak and flush catheter in preservative free saline prior to insertion
- SOC patient prep, positioning and anesthesia for lumbar puncture
- Insert epidural needle through intervertebral spinous processes to the dural level (skin nick or pilot hole may be used to help with passage of the needle)
- Remove the needle stylet and observe for CSF drainage, advance slowly until CSF is returned
- A 5ml CSF sample to be taken from the needle
 - 3ml submitted for Cell counts with Differential and Chemistries
 - 2ml for biomarkers (cytokines) which must be stored in a -80° freezer until shipped to the core lab
- An additional level or re-positioned attempt can be made if no CSF is returned
- Do not perform excessive attempts to avoid potential complications such as CSF leakage, spinal headache or nerve root damage
- Insert guidewire and advance to low-mid thoracic spine, tracking dorsally

- Remove epidural needle and leave guidewire in place
- Using an OTW technique, advance catheter over the guidewire (with tension on the end of the guidewire to prevent further advancement)
- Upon reaching the guidewire tip, advance both the wire and catheter together until the catheter proximal inlet holes rest within the lumbar cistern (approximately L2-L3)
- When the catheter is in position remove the guidewire

If there is significant difficulty in gaining access, placing or positioning the catheter, abort the procedure and dress the wound per SOC. Those Subjects who have the procedure aborted due to an inability to gain access or obtain an acceptable position are classified as an “Attempt to Treat” subject and are followed according to the protocol through 2 day follow-up to assess the wound and potential adverse events related to the attempted access or catheter insertion. Subjects in the Attempt category are exited from the study after the protocol required 2 day follow-up visit.

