 - CNS infection events will be reviewed by an independent medical monitor for whether or not the event meets the criteria above and will be used to calculate this endpoint (Number of subjects meeting CNS infection definition/Number of subjects in the Safety Population)

Secondary Efficacy endpoints:

- Mean reduction of RBCs and total protein by CSF sample post study therapy
 - This calculation utilizes the pre-Neurapheresis sample (first CSF sample taken either at the time of needle insertion or after catheter placement, whichever laboratory value is greater) as compared to the post-Neurapheresis sample (last CSF sample taken prior to catheter removal)

- Mean length of Neuro ICU stay
 - Mean length of Neuro ICU stay will be calculated by two different methods, one using physical location change, the second using criteria for critical care monitoring.

Exploratory endpoints:

- Proportion of subjects requiring additional CSF management during study therapy or on-going CSF management post study therapy
- Reduction in biomarkers of inflammation as seen in CSF, blood and physiologic manifestations post study therapy
 - Such as cytokines, white blood cell counts, neutrophil/lymphocyte ratio, SIRS
- Proportion of subjects with symptomatic complications from aSAH
 - Such as hydrocephalus, clinical vasospasm and delayed cerebral ischemia
- Analysis of endpoints by the following sub-groups for any groups that have at least 5 subjects that meet the criteria for the group;
 - Age: <45, ≥45-<60, 60 – 70 years
 - Gender: male, female
 - Enrollment Modified Fischer grade: 2, 3, 4
 - Baseline cisternal Hijdra score: ≤15, 16-20, 21-25, 26-30
 - Neurapheresis time: <16hrs, ≥16-32hrs, >32-48hrs, >48hrs
 - Other sub-groups not yet defined

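### The CSF cytokine part of the exploratory biomarker endpoint has no scheduled end-of-therapy sample: its last aliquot is at 40 h of up to 72 h in-dwelling

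*Combined protocol and SAP*

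**What the plan says.** The exploratory endpoint in section 10.2 is "Reduction in biomarkers of inflammation as seen in CSF, blood and physiologic manifestations post study therapy", with the examples "Such as cytokines, white blood cell counts, neutrophil/lymphocyte ratio, SIRS".

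Section 7.4.1 identifies what the special aliquot at catheter placement is for: "2ml for biomarkers (cytokines) which must be stored in a -80° freezer until shipped to the core lab". Table 3 in section 7.5.7 (cited in that section's text as Table 10) lists this aliquot at sample #1, with sample #2 as a fallback under footnote β, and again at sample #7. The text agrees: "CSF sample volumes are different for the initial and seventh (40 hr) sample than those in between". Samples #8 to #11 have no biomarker line.

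The same section defines the end-of-therapy specimen: "The last CSF sample taken will be considered the Final sample or (post-Neurapheresis sample) which will be compared to the Baseline sample", for the endpoint analyses to which that applies. Footnote γ covers early removal: "a final CSF sample should be taken just prior to catheter removal". That footnote is attached to sample #11, whose listed assays are cell counts with differential and chemistries.

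Section 7.5 allows the catheter to stay in for up to 72 h (±4 h) and records therapy end as the time the pump is stopped so that the catheter can be removed.

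**The concern.** The endpoint asks for change after therapy, but the second cytokine measurement is tied to a clock time, not to the end of therapy. For a subject who keeps the catheter for the full period, the 40 h value is taken while therapy may still be running. For a subject whose catheter comes out before the 40 h window opens, nothing follows the baseline.

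Cytokines appear to be the only laboratory marker handled this way. Section 7.5.8 ties venous blood and CT to 36 h and to the end of in-dwelling, and CSF cell counts, protein and glucose are taken at the final sample. At stake is whether the trial can report a post-therapy cytokine change, and whether cytokine data can inform the relation between treatment time and response that sections 4.4 and 10.2 want to build. The endpoint has no hypothesis test, so the loss is one of interpretation and completeness.

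**Working it through.** **Inputs.** Sample times, windows, volumes and assays: Table 3 and section 7.5.7. In-dwelling limit: section 7.5. Blood sampling: sections 7.1, 7.5.8 and 7.6.1. Subjects already treated: section 2.2. Earlier-study in-dwelling times: section 2.1.

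**1. Reproduce the plan's sample count.** One needle-stick sample, one after 1 h of therapy, and nine at 8-hour intervals from 8 to 72 h give 1 + 1 + 9 = 11, of which 10 fall during in-dwelling. This matches section 7.5.7. In this count 40 h is #7 and 72 h is #11, as in Table 3.

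**2. Set the assays side by side.**

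| Sample | Cell counts and chemistries | Cytokine aliquot |
|---|---|---|
| #1 placement | yes | yes (or with #2) |
| #2 to #6 | yes | no (except the #2 fallback) |
| #7, 40 h | yes | yes |
| #8 to #10 | yes | no |
| #11 or early-removal final | yes | no |

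**3. Gap at full duration.** 72 − 40 = 32 h, and 32/72 = 44% of in-dwelling time. With the ±2 h windows of Table 3 the gap runs from 70 − 42 = 28 h to 74 − 38 = 36 h. The text of section 7.5.7 gives ±1 h for samples after the 8 h one; on that reading the gap is 71 − 41 = 30 h to 73 − 39 = 34 h.

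**4. Early removal.** The 40 h window opens at 40 − 2 = 38 h (39 h under the ±1 h text). A catheter removed before then leaves no scheduled post-baseline cytokine value. If removal falls at about 38 to 42 h, the 40 h aliquot can itself serve as the end-of-therapy value.

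**5. What is measured at the end.** Cell counts in every CSF sample cover "Cell counts with Differential: RBC, WBC, neutrophils, lymphocytes, etc", so white cells and the neutrophil/lymphocyte ratio exist at the final sample, including on early removal. Blood counts with differential are taken at screening, at 36 h, at the end of in-dwelling and at the 2-day visit. SIRS does not depend on the cytokine aliquot.

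**6. Number affected.** The documents give no proportion removed before 38 h. The earlier study's maximum in-dwelling time of 36:22 h arose under a 36 h cap and cannot supply one. Purely as an assumption, if a share p of 30 treated subjects were removed before 38 h, cytokine pairs would number 30(1 − p) and the standard error of the mean change would rise by the factor √(30/n), with the same SD:

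| p (assumed) | Pairs n | √(30/n) |
|---|---|---|
| 10% | 27 | 1.05 |
| 20% | 24 | 1.12 |
| 30% | 21 | 1.20 |
| 40% | 18 | 1.29 |

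Sixteen subjects were treated under a previous protocol version, so a change now reaches about 30 − 16 = 14.

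**7. CSF volume.** Scheduled maximum now: 11 × 3 + 2 × 2 = 37 ml. With one further aliquot: 11 × 3 + 3 × 2 = 39 ml.

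**The case against.** A fixed 40 h aliquot is a defensible choice. It compares subjects at a common in-dwelling time, whereas a final-sample value mixes cytokine change with variable duration of therapy. Section 7.5.7 applies the final sample only to the analyses it suits, and section 10.2 spells out a pre/post sample rule for red cells and protein but not for biomarkers. So the schedule and the endpoint are not in outright contradiction. The 44% refers to in-dwelling time, not pump time: section 7.5 says therapy is not continuous, and the first five subjects under this version are limited to 36 h (±4 h) of pump time. The endpoint is exploratory and no decision hangs on it.

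All of this stands. It argues for keeping the 40 h aliquot, but it does not supply an end-of-therapy cytokine value.

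A reader might also infer that the biomarker reduction is never measured after therapy, or that subjects removed early have no biomarker data. Step 5 shows otherwise: named components of the endpoint are measured at the end of in-dwelling in both CSF and blood. A reader might further infer that the subjects without cytokine pairs are those who did worse. Several termination criteria in section 7.5.2 do reflect deterioration, so missingness related to clinical course is plausible. But therapy can also end by investigator or subject choice, and section 7.4 foresees catheter malfunction. The documents give no mix of reasons, so neither the direction nor the size of any selection can be stated.

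**Conclusion.** The point holds for CSF cytokines only. As scheduled, a full-duration subject has no end-of-therapy cytokine value, the last being 32 h before the final sample (28 to 36 h with Table 3 windows). A subject whose catheter is removed before about 38 h has no scheduled post-baseline value at all. These statements follow from Table 3 and need no assumption. The number of subjects affected is unknown, and the figures in step 6 are illustrations, not estimates. Because the endpoint is exploratory and untested, and the other named markers are covered, this is a cheap improvement and not a threat to the trial's main results.

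**What to change.** In Table 3, add a 2 ml CSF Biomarkers aliquot to the Final sample: #11, or the pre-removal sample under footnote γ. Keep the 40 h aliquot as a common time point; where the final draw falls in the 40 h window, one aliquot serves both purposes. Amend the sentence on sample volumes in section 7.5.7 to match.

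In section 10.2, define the post-therapy cytokine change as baseline to Final, with baseline being the placement aliquot (or #2 under footnote β). This needs stating because section 7.5.7 otherwise names #2 as the Baseline sample. Report change to 40 h alongside, with the number of subjects contributing to each and the reasons for missing values.

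Every subject with both specimens would then have a baseline-to-final pair, and a full-duration subject would have three cytokine time points instead of two. The cost is 2 ml more CSF at a draw that is already scheduled (maximum 37 to 39 ml) and one more assay per subject. Moving the aliquot instead of adding one would save that cost but lose the common 40 h comparison. If no aliquot can be added, the cytokine component should be relabelled as change to 40 h.
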